7.3.1 SUBJECT NUMBERS

Subjects will be assigned a three-digit screening number after informed consent is obtained (e.g., 001, 002, 003, etc.). Four-digit subject numbers will be allocated on the morning of dosing according to the code 1001 to 1040 using the lowest number available. Replacement subjects will be allocated subject numbers 9001 to 9040, where the last three digits are the same as those of the original subject (e.g., if Subject 1005 withdraws, the replacement will have Subject Number 9005 and will receive the same regimen as Subject 1005 with the exception of any study drugs dosed in a previous regimen that have been deemed sub-optimal).

Subject numbering by cohort is provided in Table 3.

Table 3 Subject Numbers by Cohort

| Cohort | Subject Numbers | Replacement Numbers |
|------------------|-----------------|---------------------|
| 1a.1 | 1001-1008 | 9001-9008 |
| 1a.2 | 1009-1016 | 9009-9016 |
| 1a.3 | 1017-1024 | 9017-9024 |
| 1a.4 | 1025-1032 | 9025-9032 |
| 1a.5 (if needed) | 1033-1040 | 9033-9040 |

7.4 STUDY INTERVENTION COMPLIANCE

During all clinical phases of the study, subjects will be observed by study staff to assure compliance to all study procedures, including dose administration.

The IV dose will be administered by trained staff to ensure dosing compliance.

The date and time that each subject is dosed will be recorded in the subject's eCRF. Any violation of compliance will require evaluation by the investigator and sponsor to determine if the subject can continue in the study.

7.5 CONCOMITANT THERAPY

Prescription and over-the-counter medications will be prohibited within 14 days prior to (the first) dosing and throughout the study. Over-the-counter products including natural health products (e.g., food supplements and herbal supplements) within 14 days prior to (the first) dosing, with the exception of the occasional use of acetaminophen (up to 2 g daily) are also prohibited.

The metabolic pathway of RVP-001 is not fully understood, and no formal drug-drug interaction (DDI) studies have been conducted with RVP-001. Therefore, in an effort to prevent the occurrence of any DDIs, the use of cytochrome P450 (CYP) inhibitors is prohibited for use up to 14 days prior to use of RVP-001 as stated in exclusion criteria (see Section 6.4). Also a table listing additional CYP inhibitors is provided in Section 11.4 CYP Inhibitors (FDA Table of Substrates, Inhibitors and Inducers 2020).

Subjects also cannot have depot injection or an implant (including contraception) of any drug within 3 months prior to (the first) dosing.

COVID-19 vaccines are accepted concomitant medications.

All concomitant medication use will be documented.

Medications to be reported in the Case Report Form (CRF) are concomitant prescription medications, over-the-counter medications, and supplements. Medications will be coded using World Health Organization (WHO) Drug Dictionary Global Drug Reference.

8 STUDY INTERVENTION DISCONTINUATION AND PARTICIPANT DISCONTINUATION/WITHDRAWAL

8.1 BEFORE FIRST TREATMENT ADMINISTRATION

Before the first treatment administration, inclusion/exclusion criteria will govern the subjects to be dosed. Subjects withdrawn before first treatment administration will not be followed up and will not undergo End-of-Study/Early Termination assessments.

Subjects are free to withdraw their consent to participate in the study at any time, without prejudice. The reason for their withdrawal or for deciding to end their participation will be documented.

8.2 AFTER FIRST TREATMENT ADMINISTRATION

Subjects may, at any time, voluntarily withdraw from the study or be removed from the study at the discretion of an investigator or the sponsor. An investigator may withdraw a subject at any time if it is determined that continuing the study would result in a safety risk to the subject or if their behavior is deleterious to the study environment.

If such withdrawal occurs, or if the subject fails to return for visits, an investigator should determine the primary reason for a subject's premature withdrawal from the study and record the reason in the subject's study documents. Attempts should be made to have the subject complete the End-of-Study/Early Termination assessments.

An investigator may remove a subject from the study, following consultation with the sponsor due to an unanticipated event that could result in an inadequately characterized PK profile, such as a missed blood draw or urine collection, an AE, meal deviation or concomitant medication intake.

Attempts should be made to have such subjects complete the End-of-Study/Early Termination assessments. End-of-Study/Early Termination assessments should be performed as soon as possible after the last study treatment administration.

Details of reasons for removal of subjects will be recorded, reported to the Sponsor and documented in the CSR.

Early withdrawal is defined as the date of the decision to withdraw the subject from the study. Subject completion is defined as the date of the last procedure conducted or last contact (e.g., phone call or unscheduled visit) for that subject.

8.3 STOPPING RULES

8.3.1 INDIVIDUAL SUBJECT STOPPING RULES

Participation in the clinical study may be discontinued by the physician in charge of the study or by the sponsor for any of the following reasons, but not limited to:

- AEs (including if a subject develops any significant illness or needs to undergo any major surgery during course of the study including seizure, stroke, cerebral venous thrombosis)
- Subject non-compliance (including any violation of protocol requirements which may affect the study outcome)
- 3) Subjects will be discontinued from the clinical study for any of the following reasons, but not limited to:
 - a) Meets either of the following criteria based on ECG readings:
 - 1) QTcF > 480 msec
 - 2) QTcF change from baseline >60 msec
- 4) A 7-day or 15-day IND Safety report will be submitted for any treatment emergent case of seizure, stroke, cerebral venous, thrombosis, QTc greater than 480 msec or QTC increase of more than 60 msec over baseline

For the purpose of withdrawal criteria, baseline will be considered as the last available assessment prior to first dose.

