3.2 SCHEDULE OF ACTIVITIES (SOA)

| Assessment | Screening | Admission -1 | | | Da | ys | | | Post-Treatment Phase Follow-up Phone Call 8 ³ | Subjects to Self-report AEs |
|---------------------------------------------------|-----------|-----------------|----------------|---|----|----|---|------------------|-------------------------------------------------------------------|-----------------------------------|
| Day | -28 to -2 | | 1 | 2 | 3 | 4 | 5 | 6 ^{1,2} | | 9-304 |
| Informed Consent ⁵ | x | | | | Г | | | | | |
| Eligibility criteria review (Inclusion/Exclusion) | X | X ₆ | | | | | | | j. | |
| Demographics | X | | | 3 | Ī | | | i G | 8 | |
| Medical History | X | | | | | | | | | |
| Admission to clinical site ⁷ | | Х | | | | | | | | |
| Randomization | | | X ₈ | | T | | Г | | | |
| Vital signs ⁹ | X | х | Х | Х | Х | Х | Х | Х | | |

AE = adverse event

AE = adverse event; BMI = Body Mass Index; HBsAg = surface antigen of the hepatitis B virus (HBV); HCVAb = hepatitis C virus antibodies

¹ Discharge from unit will occur after the 120-hour PK blood sample (Day 6)

² In the event of early termination, all Day 6 assessments should be performed prior to discharge.

³ Post-treatment phase follow-up phone call can be performed in a window of Day 8 +1 day

⁴ Adverse events (AEs) will be captured for 30 days post-final dose (subjects will be asked to self-report when the 30 days exceeds last follow-up). If emerging or ongoing AEs are reported at the follow-up phone call or after follow-up, additional visits and phone calls will be arranged as unscheduled visits

⁵ The latest version of the Informed Consent form must be signed prior to subject's inclusion (prior to the study drug administration on Day 1)

⁶ This is an update only of changes since screening.

⁷ Subjects will arrive at the clinical site at approximately 24 hours prior to drug administration

⁸ To be performed immediately prior to dosing

⁹ Vital signs include BP, HR, respiration rate, pulse oximetry (SpO2), and body temperature. Vital signs will be taken pre-dose (within 12 hours), at 6, 15, 30, 45, 60 minutes post dose and 2, 4, 8, 12, 24, 48, 72, 96, 120 hours post-dose for data collection. HR and pulse ox to be monitored continuously for 4 hours post-dose with any abnormal values to be followed as AEs.

| Assessment | Screening | Admission | | | Da | ıys | | | | Post-Treatment Phase Follow-up Phone Call 8 ³ | Subjects to Self-report AEs |

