9.9 SUBJECT WITHDRAWAL AND REPLACEMENT

Subjects will be advised that they are free to withdraw from the study at any time. Over the course of the study, the Sponsor and the Investigator(s) or a delegate may withdraw any subject from the study for non-compliance with protocol requirements or significant protocol deviation. Subjects may also be withdrawn by the Investigator(s) or a delegate for:

- Pregnancy [if applicable]
- Termination of the study by the sponsor, regulatory agency, or IRB
- Upon the subject's request (withdrawal of consent)
- Significant deviation from the protocol
- Significant concurrent illness or requirement for prohibited medication
- Evidence of current SARS-CoV-2 infection
- Subject non-compliance
- At the discretion of the investigator

Clinical laboratory results will be reviewed by a Medical Sub-Investigator prior to dosing, when applicable; subjects will be withdrawn from the study if it is deemed that the subject's safety may be at risk on the basis of these test results.

Subjects who withdraw or are withdrawn from the study after dosing will not be systematically replaced. However, at least 7 (out of 8) subjects from a same dose level should have completed the dosing period, and safety and tolerability data collected up to the follow up visit should be available for these subjects before the SRC can decide on dose escalation. Therefore, subjects who withdraw or are withdrawn from the study after dosing for reasons other than safety and tolerability may be replaced after consultation between the Safety Committee members. In such case, the total number of subjects dosed will remain within a maximum of 10 subjects per cohort.

Subjects withdrawn for safety reasons will be asked to remain at the clinic until the Investigator(s) or a delegate agrees that the subject is fine and can be discharged. As soon as subject withdrawal is confirmed, blood sampling will be stopped.

The minimum number of evaluable subjects is 7 per cohort. An evaluable subject is defined as a subject who has pharmacokinetic, safety, and tolerability data out to 120 hours post dose, for evaluation of the primary objective.

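### Section 8.3.1 discontinues QTcF cases after their only dose, and Section 9.9 then stops their blood sampling, so scheduled PK and safety-laboratory draws are lost in the subjects with the signal.

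*Combined protocol and SAP*

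**What the plan says.** Section 8.3.1 opens with a permissive heading: "Participation in the clinical study may be discontinued by the physician in charge of the study or by the sponsor". Item 3 of the same list is worded as mandatory: "Subjects will be discontinued from the clinical study for any of the following reasons, but not limited to". The two criteria under it are QTcF above 480 msec and a change from the last pre-dose value of more than 60 msec.

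Section 8.2 dates withdrawal from the decision ("Early withdrawal is defined as the date of the decision to withdraw the subject from the study") and sets no time limit for reaching it. Section 9.9 asks safety withdrawals to stay in the clinic until judged fit to leave, and then says "As soon as subject withdrawal is confirmed, blood sampling will be stopped".

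Footnote 2 of the Schedule of Activities (Section 3.2) says "In the event of early termination, all Day 6 assessments should be performed prior to discharge". The Day 6 column includes a PK sample and clinical laboratory tests.

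Section 9.9 also defines evaluability: "An evaluable subject is defined as a subject who has pharmacokinetic, safety, and tolerability data out to 120 hours post dose", and "The minimum number of evaluable subjects is 7 per cohort". Its escalation condition is separate: "at least 7 (out of 8) subjects from a same dose level should have completed the dosing period", with safety and tolerability data up to follow-up. That condition does not mention PK.

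**The concern.** A stopping rule for an individual normally protects the subject from further drug. Here there is none to withhold. Each subject receives a single bolus (Section 4.1) over about 5 to 15 seconds (Section 7.1.2), the first post-dose ECG is at 1 minute, and anyone with QTcF over 450 ms at screening or admission is already excluded (Section 6.4). The protocol can separate leaving treatment from leaving the study: Section 6.5.3 takes pregnant subjects off study treatment. Section 8.3.1 instead removes QTcF cases from the study, and Section 9.9 turns that into an end to blood sampling while the subject may still be resident.

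Safety is the primary objective. The regulator asked for expedited reports of these QTc events whatever their cause (Sections 4.3.3 and 9.10.12). The cohort ECG rule in Section 8.3.2 needs 3 or more subjects, so a single case does not meet it and is left to committee judgement. Section 9.12.2 asks the committee to try to relate exposure to adverse events using PK available up to 120 hours. The later concentrations and fixed-time laboratory values, including potassium and calcium (Section 9.2.1), would be missing for that case. If sampling ends before 24 hours, AUC(0-24) in Table 8 is not fully observed, and the parameters that depend on the terminal phase have little or no support.

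**Working it through.** **Inputs**

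- Post-dose PK times (Section 9.2.6; SoA footnote 20): 2, 5, 10, 20, 30 min; 1, 2, 4, 8, 12, 24, 48, 72, 96, 120 h.
- Post-dose laboratory times (SoA footnote 13): 2, 8, 24, 48, 72, 96, 120 h.
- Post-dose ECG times (SoA footnotes 15 and 16): single at 1, 3, 8 min; triplicate at 20, 40, 60 min and 2, 4, 8, 12, 24, 48, 72, 96, 120 h.

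**The plan's own figures**

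- PK samples: 1 pre-dose + 5 (2 to 30 min) + 10 (1 to 120 h) = 16, as stated, so 15 are post-dose.
- Laboratory draws after dosing, from Table 5: 2 (Day 1) + 5 (Days 2 to 6) = 7.
- Table 5 volume: 22.7 + 15.2 + 28.4 + 96.0 + 71.0 = 233.3 mL, as stated.

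**Draws lost**

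Draws lost = number of scheduled times strictly later than (time of crossing + delay until withdrawal is confirmed). The delays are assumptions.

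| QTcF crossing | Delay | PK lost (of 15) | Labs lost (of 7) |
|---|---|---|---|
| 20 min | none | 11 | 7 |
| 20 min | 30 min | 10 | 7 |
| 20 min | 2 h | 8 | 6 |
| 20 min | 4 h | 7 | 6 |
| 20 min | 24 h | 4 | 4 |
| 4 h | none | 7 | 6 |
| 4 h | 4 h | 6 | 5 |
| 4 h | 24 h | 4 | 4 |
| 24 h | none | 4 | 4 |
| 24 h | 24 h | 3 | 3 |
| 120 h | none | 0 | 0 |

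The no-delay rows are upper bounds. For the single ECGs the no-delay bounds are larger: 15, 14 and 13 PK draws at 1, 3 and 8 minutes, with all 7 laboratory draws.

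**Net of an early-termination set**

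That set returns 0 draws of each kind if Section 9.9 governs, or 1 if SoA footnote 2 does. Net PK loss:

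- 20-minute crossing: from 4 - 1 = 3 (24 h delay) to 11 - 0 = 11 (no delay).
- 24-hour crossing: from 3 - 1 = 2 (24 h delay) to 4 - 0 = 4 (no delay).

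**Evaluability**

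Any confirmation before the 120-hour draw ends PK short of 120 hours, whatever the delay, so the subject is not evaluable under Section 9.9. One case leaves 8 - 1 = 7, which meets the minimum; two leave 8 - 2 = 6, which does not. Withdrawals for a drug-related adverse event are not replaced (Section 6.2).

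The documents give no event rate. Assume a rate p in each of the 6 active subjects and none on placebo:

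- P(at least 1) = 1 - (1 - p)^6 = 11.4% at p = 2% and 26.5% at p = 5%.
- P(at least 2) = 1 - (1 - p)^6 - 6p(1 - p)^5 = 0.6% at p = 2% and 3.3% at p = 5%.

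**The case against.** The strongest reply has four parts.

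- **The rule may be discretionary.** Item 3 sits under a permissive heading, so the physician could keep the subject in and lose nothing. The item's own wording is mandatory, however, and a stopping rule open to both readings needs repair anyway.
- **Clinical care continues.** The subject stays in the clinic until judged fit, and the stay can be extended (Section 9.6). Repeat ECGs (9.1.3) and extra safety samples (9.1.1, 9.2) are allowed, and adverse events are followed until they resolve or the investigator judges it safe to stop (9.10.4). Section 9.9 stops blood only, not urine or feces collection or ECGs. This stands: clinically needed testing is not lost. But the added tests are discretionary, none restores the PK series, and the fixed ECG series is no longer clearly required.
- **Late draws may say little.** Sections 4.2 and 4.2.1 report rapid elimination in animals, so the 48 to 120 hour samples may carry little exposure information, and draws should not be weighted equally. This is fair. Yet Section 6.5 says the human half-life is unknown, which in a first-in-human study is a reason to keep the samples.
- **The footnote and Section 9.9 can be reconciled**, by reading the stop as ending serial sampling with one exit set still due. That is plausible, but the text does not say so, and one exit set does not replace the series.

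The SAP and the safety monitoring plans to which the protocol defers were not available. They may say how data from withdrawn subjects are handled, but analysis rules cannot recover samples that were never drawn. Ending research draws in a volunteer with a safety signal is a defensible instinct, and the fix leaves room for it.

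**Conclusion.** The concern holds. Followed as written, Sections 8.3.1 and 9.9 withhold no drug and cut short the scheduled PK and laboratory series in subjects with a QTcF signal. The net PK loss is 3 to 11 of 15 post-dose draws for a crossing at 20 minutes and 2 to 4 for one at 24 hours, under assumed confirmation delays of 0 to 24 hours.

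The limits are these. Samples drawn before withdrawal are kept, which will normally include the early peak; only a crossing in the first minutes with near-immediate confirmation would put it at risk. The subject stays in the safety population (Section 10.1.1) and may stay in the PK population if at least one parameter can be calculated (Section 10.1.2). Dose escalation is not shown to be blocked. The main harm is the truncated series in a single case. A cohort falling below 7 evaluable is secondary, at 0.6% to 3.3% under assumed event rates of 2% to 5%.

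**What to change.** In Section 8.3.1, take the QTcF criteria out of the permissive list and make them a separate item. A subject who meets one after dosing receives no further study drug, if any applies, but continues all scheduled safety, ECG and PK assessments to 120 hours and the follow-up call, unless consent is withdrawn or the investigator judges an assessment unsafe.

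In Section 9.9, exempt these subjects from the stop on blood sampling. Align Section 9.9 with SoA footnote 2 on whether the early-termination set includes blood. Leave the evaluability definition and the escalation condition unchanged; these subjects count only if they meet the existing definition.

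The cost is amendment wording in three places. No subjects, visits or procedures are added, and the blood is already within the planned 233.3 mL. The one drawback is continued research draws in a volunteer with a safety signal, which the consent and investigator exits address.

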8.3.2 COHORT STOPPING RULES

If any of the following safety concerns are observed, dosing of all subjects at the given dose level or higher will be suspended/halted and all available data will be evaluated by the Safety Review Committee (SRC).

- 1) If one (1) RVP-001-related SAE occurs in a cohort
- 2) Moderate or severe AEs in 50% of the subjects in the cohort or more
- Clinically significant laboratory abnormalities of the same character in 3 or more subjects (e.g., ALT >3 ULN)
- Clinically significant changes in vital signs of the same character in 3 or more subjects: BP consistently greater than 160 mmHg associated with an increase from baseline greater than 20 mmHg
- 5) Clinically significant changes in ECGs of the same character in 3 or more subjects: QTcF greater than 480 msec with an increase from baseline greater than 60 msec

Dose continuation (remaining subjects within a cohort or remaining dosing for a subject) or escalation decision will be made following evaluation of the event by the SRC.

Prior to starting a new dose/cohort, dose escalation will be discussed during the SRC meeting and may be modified or stopped depending on the investigator's or sponsor's decision, based on but not limited to the following:

- 1) New clinically significant abnormalities in physical examination, 12-lead ECG or vital signs in 2 or more subjects
- 2) Overall pattern of clinical changes or symptoms that may have appeared minor in terms of an individual AE or subject, but which collectively present a safety concern
- 3) Clinically significant changes in organ-specific laboratory parameters (e.g., liver function enzymes, renal function studies in one or more subjects)
- 4) Pattern of laboratory changes (e.g., a consistent increase or decrease within 2 or more subjects or within or across dosing groups) which might indicate an overall safety concern

In the event that a cohort is stopped due to non-drug-related events, a new cohort of additional subjects may be enrolled to replace the stopped cohort.

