8.3.3 TRIAL STOPPING RULES

Dosing and/or recruitment will be interrupted until the SRC has completed a thorough review of all available data, for any of the following reasons, but not limited to:

• If 1 subject experiences an SAE

Clinical trial stopping rules:

- If 2 RVP-001 related SAEs occur in a cohort
- If 2 subjects experience severe RVP-001 related AEs
- Occurrence of an RVP-001 related AE or SAE which results in death

Relatedness to study drug will be determined by the investigator.

If the study is halted, the IRB will be notified. The study may be resumed or terminated; however, it will not be resumed until a further notice to resume the study is submitted and approved by the IRB.

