9.12.2 CRITERIA FOR DOSE DECISIONS

Cohorts will be dosed sequentially in an ascending fashion.

Following completion of each SAD cohort, a SRC will convene to review all available blinded safety, tolerability and available PK/exposure assessments up to Day 6 (120 hours) performed for each SAD cohort, and together with attempts to correlate exposure levels with observed AEs to evaluate progression to the next dose cohort.

The SRC will be comprised of the Principal Investigator at the clinical site and the Sponsor's medical personnel, at a minimum.

Criteria for Sentinel Dosing Decision(s)

For all cohorts following a sentinel design the decision to proceed with the main group will be made by the investigator, based on safety data until 24 hours post-dose of the last sentinel subject. The investigator will inform the sponsor of any safety concerns.

For additional details refer to Data Safety Monitoring Plan (DSMP).

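### The cohort QTcF stopping rule needs both limits in a subject while individual discontinuation needs either, so three or more subjects can be discontinued for QTcF without triggering the only suspension rule that has a QTcF threshold

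*Combined protocol and SAP*

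**What the plan says.** Three rules in the protocol use the same pair of QTcF limits.

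- **Individual discontinuation, 8.3.1 item 3.** A subject is to be discontinued who "Meets either of the following criteria based on ECG readings": QTcF above 480 msec, or a change from baseline above 60 msec.
- **Expedited reporting, 8.3.1 item 4.** An IND safety report is due for "QTc greater than 480 msec or QTC increase of more than 60 msec over baseline". Sections 4.3.3 and 9.10.12 also join the limits by 'or' and make the report independent of causality.
- **Cohort suspension, 8.3.2 rule 5.** Dosing at that level or higher is suspended and the SRC reviews the data if three or more subjects have clinically significant ECG changes of the same character, defined as "QTcF greater than 480 msec with an increase from baseline greater than 60 msec". The laboratory rule in the same list gives its number as an example. Rule 5 does not, so its numbers read as the definition.

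The blood pressure rule next to it also pairs a level with a rise: "BP consistently greater than 160 mmHg associated with an increase from baseline greater than 20 mmHg". No other cohort or trial suspension rule gives a QTcF value.

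**The concern.** Every subject who counts toward rule 5 also meets the individual rule, but the reverse is not true. Discontinuations for QTcF can therefore accumulate without moving the rule 5 count.

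This matters because of the design. Each subject receives one bolus, so discontinuing someone after the dose spares nobody further exposure. Only a hold protects people who have not yet been dosed. QTc is also among the events singled out for expedited reporting in connection with the safety concerns for manganese agents (4.3.3, 9.10.12). A finding that obliges the site to discontinue the subject and the sponsor to file a report is a natural one to count toward a three-subject hold.

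**Working it through.** The plan has no figure of its own to reproduce: Section 10.2.12 says the sample size does not rest on statistical considerations. The main check is logical. The probabilities in steps 4 and 5 are illustrations.

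**1. The two triggers.** Let B be a subject's baseline QTcF, taking the 8.3.1 definition (last assessment before dosing) to apply to rule 5 as well. Eligibility caps QTcF at 450 msec at screening and admission (6.4).

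- Individual rule: QTcF > min(480, B + 60).
- Rule 5: QTcF > max(480, B + 60).
- The gap between them is |B − 420| msec wide.

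| Baseline | Individual rule met above | Rule 5 met above | Discontinued but not counted |
|---|---|---|---|
| 400 | 460 | 480 | 461–480 |
| 420 | 480 | 480 | none |
| 450 | 480 | 510 | 481–510 |

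So 400 to 470 (rise 70) and 450 to 485 (rise 35) both require discontinuation, and neither counts.

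**2. A cohort that shows the gap.** Each cohort has one active and one placebo sentinel, then five active and one placebo subject (7.3). Suppose the active sentinel goes from 400 to 455, a rise of 55 that meets neither limit. The first three active main-group subjects each go from 400 to 470. The result is three discontinuations, three expedited reports, a rule 5 count of 0 against the 3 needed, and 5 − 3 = 2 active subjects still undosed.

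**3. The other numeric cohort rule.** Rule 2 requires "Moderate or severe AEs in 50% of the subjects in the cohort or more". With the full cohort of 8 as denominator, 3/8 = 37.5% falls short and 4/8 = 50% is needed.

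**4. Size of the gain (illustration).** The documents give no human QTcF effect. Assume baseline mean 400 to 420 msec with SD 18, capped at 450, and one change per subject with SD 15. A hold helps within the cohort only if the third case is the third or fourth active main-group subject. If a subject qualifies with probability p, that has chance C(p) = p³ + 3p³(1 − p). Multiply by the chance that the active sentinel met neither limit, 1 − p(either).

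Example, mean rise 60 and baseline mean 410: p(either) = 0.563 and p(both) = 0.263.

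- Either: C = 0.412, and 0.437 × 0.412 = 0.180.
- Both: C = 0.0584, and 0.437 × 0.0584 = 0.026.

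| Mean rise (msec) | Either limit | Rule 5 as written |
|---|---|---|
| 30 | at most 0.002 | below 0.001 |
| 40 | 0.004–0.02 | below 0.001 |
| 50 | 0.05–0.10 | 0.001–0.01 |
| 60 | 0.17–0.19 | 0.008–0.05 |

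These figures suppose that the change shows on the single ECGs at 1, 3 and 8 minutes and that someone reads them before the next dose. The 8-minute ECG has a window of ±2 minutes (9.1.3), so it is recorded by minute 10. Doses are at least 15 minutes apart (7.1.2). The protocol does not say when the ECGs are read.

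**5. Size of the cost (illustration).** This is the chance that three or more of six active subjects qualify on either limit (binomial).

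- Mean peak rise 30 msec, one change per subject: p = 0.032 to 0.081, giving 0.0006 to 0.009 per cohort.
- Sustained mean rise 30 msec over the 3 single and 12 triplicate post-dose time points in the Schedule of Activities (15 in all), with the SD of 15 split equally in variance between and within subjects (15/√2 = 10.6 each): 0.10 to 0.31.
- Sustained mean rise 10 msec or less, same set-up: below 0.01.

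**The case against.** The strongest reply is that this is ordinary tiering: a sensitive rule for the individual and a more specific one for the cohort. The blood pressure rule has the same level-plus-rise form, and there is a reason for it. With 'or', a subject going from 380 to 445 msec would count although 445 lies within the protocol's own entry limit. The point stands to the extent that the wording may be intended. It is weakened because the count of three already makes the cohort rule stricter, the clinically significant qualifier would remain, and Section 8.3.1 already discontinues that subject. The blood pressure parallel is also incomplete, since 8.3.1 sets no individual blood pressure limit.

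The second reply is that other holds may act first, and a reader might infer from the gap that dosing would simply carry on. The documents do not support that inference. Section 8.3.3 interrupts dosing "If 1 subject experiences an SAE", and it contains a trial stopping rule for two subjects with severe related AEs, a lower count than rule 5. Clinically significant ECG changes are reported as AEs (9.1.3) and graded by CTCAE version 5.0 (9.10.5). If such a rise were graded severe and judged related, the example in step 2 would meet that trial rule at the second subject. The term-level grades are not in the documents, so this cannot be settled here. Rule 1 covers a related SAE, the interruption list in 8.3.3 is expressly open-ended, and Section 11.1.4 allows suspension for unacceptable risk. All of these safeguards stand, but each turns on grading, seriousness, relatedness or discretion.

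A reader might also infer that escalation would go ahead after three such discontinuations. That does not follow either. The SRC reviews the data before each new dose and may act on new clinically significant ECG abnormalities in two or more subjects (8.3.2). Section 9.9 also expects that "at least 7 (out of 8) subjects from a same dose level should have completed the dosing period", with safety data to follow-up, which could itself delay escalation. For the sentinel stage, "the decision to proceed with the main group will be made by the investigator". No QTcF threshold is stated there, although a Data Safety Monitoring Plan that is not among the documents may add one.

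**Conclusion.** The mismatch is in the current text and its consequence is deterministic: for any eligible baseline other than 420 msec there is a range of QTcF values that forces discontinuation and adds nothing to rule 5. It would go too far to call this an error or a contradiction, because the rules can operate together and requiring both limits may be deliberate.

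The point is minor. The benefit is confined mainly to undosed subjects in the same cohort and depends on prompt ECG reading. In the illustration it is negligible at a mean rise of 30 msec, small at 40, and material only from about 50. Those figures rest on assumed distributions and treat each cohort alone, without the SRC's review of lower doses. The logical finding does not depend on them.

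**What to change.** In 8.3.2 rule 5, keep the clinically significant qualifier and the count of three. Replace "QTcF greater than 480 msec with an increase from baseline greater than 60 msec" with: *QTcF above 480 msec or an increase from baseline above 60 msec (QTcF prolongation by either criterion is the same character)*. Leave the consequence as it is, suspension pending SRC review.

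The cost is one line of text and more SRC reviews, as sized in step 5. Reviews would become common only with a large effect such as a sustained 30 msec rise, and that would merit review in any case.
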